There are numerous interventions that are associated with reduction in the incidence, severity or both of pain or a reduction in analgesia requirements for women having surgical laparoscopy for gynecological purposes.⁽⁸⁾ These could be medical or surgical or even technical interventions that has been developed in an attempt to reduce postoperative pain after surgical laparoscopy as an example of those interventions developing a specific technique for releasing pneumoperitoneum; humidification of gas used in pneumoperitoneum reducing the pressure used to inflate the abdomen,⁽⁹⁾ also novel techniques regarding intraperitoneal fluid instillation using isotonic saline; an intra-peritoneal drain in an attempt to eliminate any residual fluid or gas; and local anesthetic applied to the peritoneal cavity to reduce nerve irritation of the peritoneal and visceral nerves.⁽¹⁰⁾

Bupivacaine, is a local anesthetic. In nerve blocks, it is injected around the nerve that supplies a certain area, or into the spinal canal's epidural space,⁽¹¹⁾ bupivacaine binds to the intracellular portion of voltage-gated sodium channels and blocks sodium influx into nerve cells, which prevents depolarization. Without depolarization, no initiation or conduction of a pain signal can occur.⁽¹²⁻¹⁴⁾

Hence the idea of our study is to instill bupivacaine in a certain concentration in the peritoneal cavity in an attempt to reduce postoperative pain after surgical laparoscopy for gynecological purposes that will inflect certainly on patient's hospital stay and mobility.

AIM OF THE WORK

The aim of the present study is to:

Primary

1. Evaluate the efficacy of instilling bupivacaine intraperitoneal in reducing postoperative pain after surgical laparoscopy for gynecologic procedures.

Secondary

1. Assessment of the timing passed postoperative, since the patient needs to start the first analgesic dose.
2. Frequency of analgesia requested by the patient in postoperative period.
3. Assessment of the time passed postoperative since the patient start mobility.

PATIENTS

This randomized controlled trial will be conducted for (80) women undergoing laparoscopic procedures at endoscopy unit at El-Shatby Maternity University Hospital, after approval of ethical committee of Alexandria Faculty of Medicine.

Inclusion Criteria:

- 1- Patients those are indicated for surgical laparoscopy, whatever the gynecological problem.
- 2- Age between (18-50) years.

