- 3- Cooperative patient that can express pain and score it.

Exclusion criteria:

- 1- Non-cooperative patients that cannot express and score pain.
- 2- Drug abusers due to altered pain threshold.
- 3- Surgical laparoscopy indicated for oncological procedures.
- 4- Any allergy or reaction to any of the derivatives of bupivacaine drug group.
- 5- Any cardio-pulmonary condition.

Randomization will be through opaque sealed envelopes.

METHODS

After signing their informed consents, the patients who are included in the study will be divided into two groups each group include (60) patients.

Group A: Patients that will receive intraoperative instillation of bupivacaine.

Group B: (Control group) that will not receive the medication.

The patients in both groups will be subjected to:

Pre-operative:

History taking (gynecological, obstetric, medical any drug reaction and surgical), general examination and abdominal examination.

Intra-operative:

premedication : 1.5 microgram/kg fentanyl IV

induction of anesthesia: 2mg/kg Propofol IV , 0.5 mg/kg Atracurium IV , ventilation via face mask 2-3 minutes , then endotracheal intubation

1gm paracetamol IV as intraoperative analgesia which will not interfere with postoperative pain scoring.

Group (A) only will receive intra-peritoneal 40 ml bupivacaine 0.2%, after laparoscopic procedure before removing trocars.

Post-operative (Outcome variables):

- 1- Assessment of the postoperative pain at 2h, 8h ,24h respectively by visual analogue score (VAS).
- 2- Assessment of the timing -in hours- of analgesia initiation postoperatively -when VAS score is 4 or more-, non-steroidal analgesia ketorolac 30 mg will be used.
- 3- Assessment of the frequency of analgesic need postoperatively.
- 4- Assessment of the timing-in hours- of mobility initiation postoperatively.

Every patient will be asked by the data collector, in order to fulfill the following -appendix- sheet postoperative.

ETHICS OF RESEARCH

Research on human or human products:

- Prospective study: Informed consent will be taken from patients. In case of incompetent patients, the informed consent will be taken from the guardians.
- Retrospective study: Confidentiality of records will be considered.

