- DNA / genomic material: Informed consent for DNA/genomic test and for research will be taken from patients. No further tests will be carried out except with further approval of committee and patients. If the samples will travel outside Egypt the researcher will be responsible for transportation and security approval.
- All drugs used in the research are approved by the Egyptian Ministry of Health.

Research on animal:

- The animal species are appropriate for the test.
- After test, if the animal will suffer, it will be euthanized and properly disposed.
- After operation, it will have a proper postoperative care.

سأقوم بتسلیم الموناقات المبنیة على علم المريض الخاصة بالدراسة عند الانتهاء منها أو
عند طلبها من اللجنة

RESULTS

The results will be tabulated and statistically analyzed, using the standard statistical methods.

Statistical analysis of the data

Data will be fed to the computer and analyzed using IBM SPSS software package version 20.0. (Armonk, NY: IBM Corp) Qualitative data were described using number and percent. The Kolmogorov-Smirnov test will be used to verify the normality of distribution Quantitative data were described using range (minimum and maximum), mean, standard deviation, median and interquartile range (IQR). Significance of the obtained results will be judged at the 5% level.

The used tests were

1 - Chi-square test

For categorical variables, to compare between different groups

2 - Fisher's Exact or Monte Carlo correction

Correction for chi-square when more than 20% of the cells have expected count less than 5

3 - Student t-test

For normally distributed quantitative variables, to compare between two studied groups

4 - Mann Whitney test

For abnormally distributed quantitative variables, to compare between two studied groups

5 -Wilcoxon signed ranks test

For abnormally distributed quantitative variables, to compare between two periods

DISCUSSION

The results will be discussed in view of achievement of the aim and will be compared with available literature and published data

REFERENCES

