APPENDIX

Evaluation sheet of post-operative pain

Patient name:

Date:

Registration number:

Mobile number:

Operation undergone:

[figure not shown]
Time exiting the OR:

Time of first analgesia:

[figure not shown]
Frequency of analgesia:

Time of first mobility:

[figure not shown]
2h. post-operative (.....)

8h. post-operative (.....)

24h. post-operative (.....)

No pain (0), Mild (1-3), moderate (4-6), severe (7-9), worst pain (10), start analgesia at threshold -moderate pain- which is score 4.

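### Time to first analgesia has no value for women who never need a dose, and the planned t-test or Mann-Whitney comes with no censoring or ranking rule for them

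*SAP*

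**What the plan says.** The SAP, under AIM OF THE WORK, lists as its first secondary aim "Assessment of the timing passed postoperative, since the patient needs to start the first analgesic dose". METHODS, Post-operative (Outcome variables), item 2, makes this a variable in hours tied to a pain threshold: "Assessment of the timing -in hours- of analgesia initiation postoperatively -when VAS score is 4 or more". The APPENDIX sheet repeats the threshold ("start analgesia at threshold -moderate pain- which is score 4"). It has one blank for "Time of first analgesia" and another for "Frequency of analgesia", and no entry for a woman given nothing.

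Pain is assessed at three times, the last at 24 h: "Assessment of the postoperative pain at 2h, 8h ,24h respectively by visual analogue score (VAS". No end of observation is stated for the time to analgesia.

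Under RESULTS, Statistical analysis of the data, a Kolmogorov-Smirnov check decides between the t-test (item 3) and the Mann-Whitney test (item 4), the latter "For abnormally distributed quantitative variables, to compare between two studied groups". The summaries are given as "Quantitative data were described using range (minimum and maximum), mean, standard deviation, median and interquartile range (IQR". The SAP contains no survival method, censoring time, ranking rule or missing-data rule.

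**The concern.** The outcome exists only for women who receive a dose. Every listed test and summary needs a number for each woman, and a never-rescued woman has none. With a blank cell she is dropped, and what remains is a comparison of rescued women. Whether a woman is rescued is itself a result of treatment, so that comparison is no longer protected by randomisation. If bupivacaine works by sparing women any rescue, the women who benefit most are the ones removed, and the benefit does not show in this outcome.

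Entering 24 h for these women is not a full repair. The mean and SD would treat a limit as an observed time. A dose triggered by the 24 h assessment would then tie with women who needed nothing, or rank after them.

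The handling is left open, so it could be chosen after the data are seen. At stake is the first-listed secondary outcome, not the primary.

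**Working it through.** **Inputs from the SAP.** Dosing threshold VAS 4 or more; last assessment at 24 h; significance level 5% (two-sided assumed). The SAP states both 80 women in total (80 / 2 = 40 per arm) and 60 per group, so results are given for 40 / 60 per arm. It states no rescue rate, effect size or power, so there is no figure to reproduce. Its introduction says pain occurs in up to 80% of women. That is any pain, not VAS 4 or more, and is not used as a rescue rate.

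**Assumed.** Rescue rates, exponential rescue times and a 24 h window. Rates and mean times are given as bupivacaine v control.

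**Who is lost.** With 50% v 80% rescued at 40 per arm, 0.50 × 40 + 0.80 × 40 = 20 + 32 = 52 women are analysed and 28 of 80 are dropped. At 60 per arm, 30 + 48 = 78 are analysed and 42 of 120 are dropped.

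**Tests compared.** Mann-Whitney: z = (U − n₁n₂/2) / SD(U), tie-corrected, first among rescued women only and then in all women with the never-rescued sharing one last rank. Log-rank: z = (O − E) / √V, censored at 24 h. There were 4,000 simulated trials per cell; the 95% error is at most 1.96 × √(0.25 / 4000), about 1.5 points.

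Power in %, at 40 / 60 per arm:

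| Rescued; mean time | Rescued only | Ranked last | Log-rank |
|---|---|---|---|
| 65 v 65%; 4 v 4 h (null) | 4.4 / 5.2 | 4.9 / 4.6 | 5.2 / 4.9 |
| 50 v 80%; 4 v 4 h | 5.0 / 5.2 | 67.2 / 83.9 | 78.6 / 92.2 |
| 70 v 90%; 4 v 4 h | 4.9 / 4.8 | 34.8 / 47.9 | 54.0 / 71.2 |
| 85 v 95%; 4 v 4 h | 5.1 / 5.4 | 11.8 / 15.2 | 22.4 / 30.3 |
| 70 v 90%; 6 v 4 h | 24.1 / 35.4 | 72.6 / 88.3 | 79.4 / 92.8 |
| 98 v 99.8% by 24 h; 6 v 4 h | 30.8 / 43.2 | 34.6 / 48.7 | 42.8 / 61.2 |

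Where timing among the rescued is equal, the rescued-only test stays at 5% by construction.

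**A second model, checkable by hand.** Let 20% of controls be unrescued at 24 h, with a constant hazard and a hazard ratio of 0.5. The unrescued share on bupivacaine is then 0.20^0.5 = 0.447.

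- Control mean: λ = −ln(0.20) / 24 = 0.0671 per hour, so 1/λ = 14.9 h. On bupivacaine it is 29.8 h.
- Mean among the rescued = 1/λ − 24p / (1 − p), where p is the unrescued share. Control: 14.9 − 24 × 0.20/0.80 = 8.9 h. Bupivacaine: 29.8 − 24 × 0.447/0.553 = 10.4 h. Halving the hazard appears as a difference of about 1.5 h.
- Log-rank power = Φ(|ln 0.5| × √d / 2 − 1.96). At 40 per arm, d = 40 × (0.80 + 0.553) = 54.1 events, giving Φ(0.59) = 72%. At 60, d = 81.2, giving Φ(1.16) = 88%.
- Simulation of this model (1,500 trials) gives the same log-rank power, 72 / 88%. Ranked last gives 67 / 85%, rescued-only Mann-Whitney 12 / 17% and rescued-only t-test 13 / 18%.

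**Coding 24 h.** If rescue is found only at the 2, 8 and 24 h assessments (50 v 80%, same timing), about 9% of women are dosed at 24 h. Coding the never-rescued as 24 h gives 58.6 / 76.2% power, against 68.5 / 85.8% when they rank beyond every recorded time.

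**The case against.** The SAP does not say that unrescued women are excluded, nor that a dose is impossible below VAS 4; its second secondary aim speaks of analgesia the patient requests. Mann-Whitney is valid if these women rank last, so what is missing is a rule rather than a test. That is fair, but the rule appears nowhere, and a blank time run through the listed tests drops the woman.

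Frequency of analgesia already captures rescue sparing, since such a woman scores zero. This stands and limits the harm to one secondary outcome.

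Part of the log-rank gain has nothing to do with dropped women. With every woman rescued at means of 6 v 4 h, a check gave Mann-Whitney about 34 / 50% and log-rank 41 / 59%, because exponential times favour log-rank. This also stands: the cost of dropping women should be read from rescued only against ranked last.

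The 24 h loss arises only if doses are triggered at the assessments. The sheet records a separate clock time, and with continuous times below 24 h, coding 24 h gives the same ranks as ranking last. The point is therefore conditional.

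Finally, the simulations show lost power, not a biased or reversed result, and all rates are assumed. Both are true. The loss of the randomised comparison follows from the selection itself and does not depend on those rates.

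**Conclusion.** The concern holds. The SAP defines a time that some women may never have, lists only tests that need a value from every woman, and gives no rule to bridge the two.

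The size depends on how many women go without rescue and how far the arms differ in that. Comparing rescued only with ranked last, power at 40 per arm is 5% against 67% when rescue is 50 v 80% with equal timing, and 31% against 35% when almost all are rescued. At 85 v 95% even the repaired analyses reach only 12 to 30% across the two sizes, so the practical gain can be modest. These figures rest on assumed rescue rates, exponential times and a 24 h window.

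The primary VAS outcome and the frequency of analgesia are unaffected. It should be corrected before the data are analysed.

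**What to change.** Add to the SAP, under Statistical analysis of the data:

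> Time from leaving the operating room to first postoperative analgesia will be analysed in all randomised women by Kaplan-Meier and log-rank test. Women given no analgesia are censored at the end of a stated observation window (the last planned assessment is 24 h), or at last observation if earlier. A dose triggered by the 24 h assessment counts as an event within the window. Medians, and the number and percent given analgesia, are reported per group, not mean and SD.

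Add that a median not reached is reported as such. With 50% rescued this happened in about 44 to 45% of simulated trials, so the proportion given analgesia must stand beside it.

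A simpler option, if every woman is observed to the end of the window, is to keep the listed Mann-Whitney test and give never-rescued women one common rank beyond every recorded time.

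In both, identify these women by a frequency of analgesia of zero; a separate entry for none given is optional.

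The cost is a few sentences and one standard procedure, or no new procedure with the ranking option. Time leaving the operating room, time of first analgesia and frequency are already on the sheet. The only added item is the time of last observation for a woman who leaves before the window ends.

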APPENDIX

Evaluation sheet of post-operative pain

Patient name:

Date:

Registration number:

Mobile number:

Operation undergone:

[figure not shown]
Time exiting the OR:

Time of first analgesia:

[figure not shown]
Frequency of analgesia:

Time of first mobility:

[figure not shown]
2h. post-operative (.....)

8h. post-operative (.....)

24h. post-operative (.....)

No pain (0), Mild (1-3), moderate (4-6), severe (7-9), worst pain (10), start analgesia at threshold -moderate pain- which is score 4.
